2.6 Sample Size and Randomization

A sample size of 256 participants (n=128 per each trial arm) will have sufficient power (80%) to detect an

average between-group difference with a moderate effect size of Cohen's $d = 0.4$. The mixed effect modeling for repeated outcome measures at 6 and 12 months was used for the power calculation using two-sided significance level of 0.05 assuming 1) first-order autoregressive covariance structure, 2) the within-structure correlation of 0.8, and 3) 20% attrition rate at 12-month follow-up. After completing the informed consent and baseline data collection, participants will be randomly assigned 1:1 to the intervention or the attention-control group. Stratified randomization by sex (female vs. male) and ethnicity (Non-Hispanic Black vs. Hispanic Black) will be used. For each sex-ethnicity stratum, randomization will occur in permuted blocks of varying block sizes. The advantage of permuted block randomization is that it will ensure balance in the number of participants in the two trial arms during the entire study period.

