3.9 Systems of Support

Project staff are provided cell phones to enable accessible and timely communication with participants in regarding technological issues, scheduling, and other emergency circumstances. Acknowledging the various social determinants of health that CC students of color experience, project staff have designed an ecosystem of support in collaboration with the community college to enable access to mental and physical health, financial, educational, and housing services if requested by the student. If students screen positively for suicidal ideation on the administered PHQ-9, they are immediately connected to services and study staff follow up with participants until they participate in their first appointment. Additionally, project staff are trained in Mental Health First Aid to equip them with the tools and skills to manage a mental health crisis in a young adult, e.g. recognizing signs and symptoms, how to listen non-judgmentally and give reassurance, and how to refer someone to appropriate services.

4. Measurements

The study team will collect outcome measure data (Tables 3 and 4) from all participants at in-person or Zoom visits at baseline (prior to randomization), 6- and 12-months. The project coordinator and research assistant are not blinded to the treatment condition. At the conclusion of the 12-month visit, participants complete a quality assessment survey to detail their satisfaction with or suggestions for the program.

Table 3: Main Outcome Measures

Outcome	Time Measured	Definition	Measurement Procedure	Measurement Tool
---------	---------------	------------	-----------------------	------------------

Weight	Baseline, 6 and 12 months	Body weight (kilograms)	Wears light clothing, no shoes; 2 measurements taken and averaged	Tanita BS-549 Ironman Scale
Percent Weight Loss	6 and 12 months	Comparison of current weight to baseline weight, then convert to % of baseline weight	Same as above	Same as above
Weight Loss Maintenance	12 months	Sustained weight loss of 5- 10% of baseline body weight OR maintenance of % weight lost at 6-months	Same as above	Same as above
Height	Baseline	Length of individual (meters)	Same as above	Seca 213 portable stadiometer
Body Mass Index	Baseline, 6 and 12 months	Weight to height ratio	Height and weight of participant	Quetelet index (kg/m ²)

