Depressive Symptoms (moderator)	CDE Patient Health Questionnaire for adults (PHQ-9)	10 questions that assess depressive symptoms. Questions are scored on a 0-3 scale. Total scores range from 0 (no depression) to 27 (severe depression).	Reliable and valid in a diverse group of adults over 18, with a Cronbach alpha reported at 0.89 and 0.86 in two studies and a test-retest score of 0.84. ²³
Ideal Body Image (moderator)	Contour Drawing Rating Scale	Contour drawing of graduated sizes, with 9 images for males and 9 images for females. ²⁴ Participants will circle the figure that represents their ideal body image.	Test-retest reliability was confirmed in college students with a reliability rating of 0.78 and validity was confirmed in college students with 95% accuracy in correct ordering of images. ²⁴
Motivation (moderator)	Treatment Self-Regulation Questionnaire (TSRQ)	15 questions to assess diet and 15 questions to assess exercise. The TSRQ measures three	The TSRQ for diet and exercise was proven reliable in a racially/ethnically diverse group of males and females, aged 18+ years,

		types of motivation: (1) controlled, (2) autonomous, and (3) amotivation.	with Cronbach alphas >0.73. ²⁵
Emotional Support (moderator)	NIH PROMIS tool for emotional support (16 questions)	Assesses perceived feelings of being cared for and valued as a person and having confidant relationships	Questionnaire has been validated in adult populations. ²⁶

6. Statistical Analysis

Aim 1: Descriptive statistics will be used to check the distribution of the data, identify outliers, and describe the sample characteristics. Bivariate statistics will be used to compare baseline characteristics between the two trial arms. We will use mixed-effects linear regression modeling for repeated measures to 1) estimate the fixed effects of intervention, time, and their interactions, 2) derive contrast estimates for between-group differences in % weight loss at 6 months and 12 months, 3) adjust for covariates (e.g., any imbalance in baseline characteristics) and within-subject dependency from repeated measures.²⁷ All tests will be performed using Intent-to-Treat (ITT) analysis.

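### Baseline weight is not a prespecified covariate in the Aim 1 percent-weight-loss model; it enters only if the arms look imbalanced, and it is not named for the imputation model

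*Combined protocol and SAP*

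**What the plan says.** Section 6, Aim 1, first has the arms compared on baseline characteristics. It then describes a mixed-effects linear model that will "estimate the fixed effects of intervention, time, and their interactions", give between-arm contrasts in percent weight loss at 6 and 12 months, and adjust for covariates. The only example of a covariate is a baseline characteristic found to be imbalanced. Baseline weight and BMI are not named.

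Table 3 in Section 4 defines percent weight loss as "Comparison of current weight to baseline weight, then convert to % of baseline weight", measured at 6 and 12 months. Section 2.6 matches this: "The mixed effect modeling for repeated outcome measures at 6 and 12 months was used for the power calculation". Baseline is therefore not an occasion in the repeated-measures model for this outcome. Randomisation is stratified by sex and ethnicity, not by weight or BMI.

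The missing-data paragraph of Section 6 provides for multiple imputation if data are missing at random, pattern mixture modelling if not, and sensitivity analyses. It does not list the variables in the imputation model.

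**The concern.** Whether baseline weight is in the primary model is decided after the arms have been compared. That rule has three weaknesses.

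- It reacts to observed imbalance and ignores how strongly the variable predicts the outcome.
- It can leave in the estimate a chance difference that was too small to be flagged.
- It leaves the primary model open until baseline data have been examined by arm.

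The definition of the outcome does not replace adjustment. Write W0 for baseline weight and W1 for follow-up weight, and suppose the mean of W1 given W0 is a + k·W0. Treating W0 as given, expected percent loss is 100(1 − k) − 100a/W0. This is free of W0 only if a = 0, that is, if follow-up weight is exactly proportional to baseline weight.

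At stake are some precision, exposure to unflagged chance imbalance, and protection against one kind of dropout. A participant with no post-baseline visit contributes nothing to a model of percent loss, so only baseline variables and arm can inform that person's imputed values.

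**Working it through.** **Inputs.** From Section 2.6: 128 per arm, d = 0.4, "two-sided significance level of 0.05", 20% attrition at 12 months, 80% power. The correlation r between baseline weight and percent loss is not in the documents, so r = 0.1, 0.2 and 0.3 are assumed. Section 2.6 also states "the within-structure correlation of 0.8". That refers to the repeated outcome and must not be used as r.

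**1. The stated power.** Completers per arm: 128 × 0.8 = 102.4, taken as 102. Noncentrality: 0.4 × √(102/2) = 2.857 on 202 degrees of freedom. Two-sided t-test power: 81.1%. In reverse, 80% power needs 100 per arm, and 100/0.8 = 125, or 250 in total against the planned 256. The stated 80% is thus reproduced by a single-visit comparison of completers with no covariate.

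**2. Precision.** Adjustment multiplies the residual variance by 1 − r², so the effective effect size is 0.4/√(1 − r²).

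| r | Variance reduction | Effective d | Power, 102 per arm |
|---|---|---|---|
| 0 | 0% | 0.400 | 81.1% |
| 0.1 | 1% | 0.402 | 81.5% |
| 0.2 | 4% | 0.408 | 82.7% |
| 0.3 | 9% | 0.419 | 84.6% |

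The gain is 0.4 to 3.5 percentage points.

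**3. Chance imbalance.** The plan gives no threshold for calling a characteristic imbalanced; a 5% test is assumed. A difference at that limit is 1.96 × √(2/128) = 0.245 SD of baseline weight. The unadjusted estimate shifts by r × 0.245:

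- r = 0.1: 0.025 SD, or 6% of d = 0.4
- r = 0.2: 0.049 SD, or 12%
- r = 0.3: 0.074 SD, or 18%

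Differences just below the limit would go unflagged. Over repeated randomisations such shifts average to zero, so this is a matter of precision in the trial at hand and not of systematic bias.

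**4. Dropout.** Simulation with 128 per arm, about 20% dropout, a true effect of 0.40 SD that is the same at every weight, and dropout log-odds changing by 0.8 per SD of baseline weight. Completers are analysed without imputation.

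| Dependence of dropout on baseline weight | Unadjusted estimate at r = 0.1, 0.2, 0.3 | Adjusted |
|---|---|---|
| Same in both arms | 0.40, 0.40, 0.40 | 0.40 |
| One arm only | 0.39, 0.38, 0.36 | 0.40 |
| Opposite by arm | 0.43, 0.46, 0.49 | 0.40 |
| Opposite by arm, signs swapped | 0.37, 0.34, about 0.31 | 0.40 |

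At r = 0 there is no bias under any pattern. If the treatment effect itself varied with baseline weight, dropout on the same pattern in both arms could also move the unadjusted contrast. That case was not simulated.

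**The case against.** The strongest reply is that the plan already takes account of baseline weight. The outcome is scaled by it, the covariate clause allows adjustment for imbalance and its example is not exhaustive, and imputation, pattern mixture models and sensitivity analyses are all planned. Much of this stands, and it rules out several stronger readings that a reader might infer.

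- *That the model omits the baseline value of its own outcome.* Percent weight loss is zero for everyone at baseline and has no baseline value to include. Baseline weight is a separate prognostic covariate of unknown strength.
- *That chance baseline differences necessarily stay in the estimate.* Flagged differences would be adjusted for. Only unflagged ones may remain.
- *That dropout related to baseline weight biases the result.* Baseline weight must also predict percent loss, and the dropout relation must differ by arm or the effect must vary with weight. The documents give no evidence of either pattern, although the arms receive different contact (daily coach messages against sleep tracking). Imputation that included baseline weight could deal with an arm-specific relation; the plan does not say whether it will be included.
- *That large gains are being lost for active minutes and diet score.* At assumed baseline correlations of 0.5 to 0.7, adjustment would cut variance by 25% to 49% against a follow-up-only contrast (1 − r²), or by 25% to 15% against a change contrast ((1 + r)/2). But Section 6 writes contrasts only for percent weight loss. These other outcomes are measured at baseline, so a repeated-measures model could hold baseline as an occasion. The figures rest on assumed correlations and an inferred model.

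What survives is that the adjustment is triggered by data rather than prespecified, and that the imputation variables are not stated.

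**Conclusion.** The point holds as a free improvement of low to moderate priority. It does not show that the trial is underpowered or that its estimate is biased.

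The precision gain is probably small, and it rests wholly on correlations that the documents do not give. The possible shift from an unflagged imbalance is larger relative to the effect, but it too scales with r and rests on an assumed 5% flagging rule. The dropout shifts of up to about 0.09 SD at r = 0.3 come from deliberately unfavourable opposite-direction patterns analysed without imputation, and they show what is possible, not what is expected.

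The firmest reason to act does not depend on r: the covariate set of the primary model should not wait for a comparison of the arms.

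**What to change.** In Section 6, Aim 1, replace imbalance-triggered adjustment with a fixed statement: the percent-weight-loss model will include baseline weight (continuous) and its interaction with time, whatever the observed balance. The interaction lets the association with baseline weight differ between 6 and 12 months. In the missing-data paragraph, name baseline weight as a variable in the imputation model.

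If active minutes, diet score or BMI are to be analysed with the same type of model, prespecify the baseline value of each as a covariate. The gain there cannot be sized from the documents.

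The cost is a sentence or two in Section 6. Baseline weight is already measured before randomisation, so no new data, visits or participants are needed, and the sample size stands.

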2.3 Design

Participants will be randomized with equal allocation to a 12-month intervention that includes using a smartphone app and text messages from a health coach or to an attention-control condition. In total, 256 individuals will be enrolled and randomized with a target of 80% Non-Hispanic Black, 20% Hispanic Black with 50% male representation in each ethnic group. Participants will be enrolled from a community college in Columbus, OH. The intervention will be delivered via a smartphone and the health coach will send the text messages. This study employs an attention-control condition to keep control participants engaged in the study and have them return for data collection visits. Considering the limited number of studies describing recruitment and retention methods for this population, an attention-control condition rather than a standard control condition is warranted. The study was approved by the Institutional Review Board (IRB) at The Ohio State University (OSU).

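### The Aim 1 primary model does not commit to adjusting for sex and ethnicity, the two randomisation strata, and its covariate list is open

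*Combined protocol and SAP*

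**What the plan says.** Section 2.6 sets out the randomisation: "Stratified randomization by sex (female vs. male) and ethnicity (Non-Hispanic Black vs. Hispanic Black) will be used". It continues: "For each sex-ethnicity stratum, randomization will occur in permuted blocks of varying block sizes". Section 2.3 gives the intended mix, a "target of 80% Non-Hispanic Black, 20% Hispanic Black with 50% male representation in each ethnic group".

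Section 6, Aim 1 describes the primary analysis. The mixed model will "estimate the fixed effects of intervention, time, and their interactions", "derive contrast estimates for between-group differences in % weight loss at 6 months and 12 months", and "adjust for covariates (e.g., any imbalance in baseline characteristics) and within-subject dependency from repeated measures". Just before this, the plan states: "Bivariate statistics will be used to compare baseline characteristics between the two trial arms".

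No covariate is named and no criterion for imbalance is given. Sex and ethnicity appear in no model in section 6, whether under Aim 1, Aim 2, Aim 3 or missing data.

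**The concern.** A factor used to stratify randomisation normally belongs in the primary model. Stratified blocking lowers the true variance of the treatment contrast when the strata predict outcome. A model without the strata still reports the larger variance, so the test is conservative and some of the precision bought by the design is thrown away.

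Here the only stated example of a covariate is one found imbalanced at baseline. Sex and ethnicity are the two characteristics least likely to meet that description, because the blocks keep them balanced.

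There is also a pre-specification problem that does not depend on how strongly the strata predict outcome. With an open list and no threshold, several different primary models would all fit the plan, and the choice could be made after the arms have been compared. Aim 2 refers back to the same mixed models, so the ambiguity carries forward.

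**Working it through.** **Inputs from the documents.** 128 per arm, d = 0.4 (so SD = 1), two-sided 5%, and the section 2.6 assumptions, "assuming 1) first-order autoregressive covariance structure, 2) the within-structure correlation of 0.8, and 3) 20% attrition rate at 12-month follow-up". The section 2.3 mix applied to 256 gives strata of about 102, 102, 26 and 26.

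**Assumptions.** Dropout is random. Block sizes are 2, 4 and 6 (the plan says only that they vary). R², the share of outcome variance explained by sex and ethnicity, runs from 0 to 0.10 and is the same at both visits. The documents give no R².

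**Step 1: the plan's own figure.** Single time point, normal approximation: n = 2(1.960 + 0.842)²/0.4² = 98.1, so 99 per arm. Then 99/0.8 = 123.75, so 124 per arm and 248 in total. The noncentral t gives 100 per arm, 100/0.8 = 125, and 250 in total. With 128 × 0.8 = 102.4 completers per arm, power is 81.7% (normal) or 81.3% (t). The stated 256 for 80% power is therefore consistent with its inputs.

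**Step 2: would the imbalance example select the strata?** In 10,000 stratified randomisations, the largest arm difference in the proportion of either sex or either ethnicity was 3.1 percentage points.

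**Step 3: single time point, 102 completers per arm.** SE0 = √(2/102) = 0.140. Random loss of 20% partly undoes the balance, so:
- the true SE of the unadjusted contrast is SE0·√(1 − 0.8R²);
- the unadjusted model reports SE0;
- the adjusted SE is SE0·√(1 − R²).

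The SE ratio (reported over true) is 1/√(1 − 0.8R²), and the actual type I error is 2[1 − Φ(1.96 × SE ratio)]. Unadjusted power is Φ((0.4 − 1.96·SE0)/true SE). Adjusted power is Φ(0.4/adjusted SE − 1.96).

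| R² | SE ratio | Type I, unadjusted | Power, unadjusted | Power, adjusted |
|---|---|---|---|---|
| 0 | 1.000 | 5.0% | 81.5% | 81.5% |
| 0.02 | 1.008 | 4.8% | 81.7% | 82.3% |
| 0.05 | 1.021 | 4.55% | 82.0% | 83.4% |
| 0.10 | 1.043 | 4.1% | 82.5% | 85.3% |

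Simulation (100,000 trials per case, 205 random completers) agrees. Type I error, unadjusted and adjusted, is 4.6% and 5.1% at R² = 0.05, and 4.1% and 5.0% at 0.10. Power is 81.9% and 83.2% at R² = 0.05, and 82.3% and 85.2% at 0.10.

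**Step 4: planned repeated-measures model, 12-month contrast.** Take all 256 as seen at 6 months and 205 at 12 months, the most favourable case. With correlation 0.8, SE = √[2(0.36/102.4 + 0.64/128)] = 0.1305, and power at R² = 0 is 86.5%. Simulation gives:

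| R² | Power, unadjusted | Power, adjusted | Type I, unadjusted | Type I, adjusted |
|---|---|---|---|---|
| 0 | 86.0% | 86.0% | – | – |
| 0.02 | 86.5% | 86.9% | – | – |
| 0.05 | 86.8% | 87.7% | 4.5% | 5.1% |
| 0.10 | 87.4% | 89.4% | 4.0% | 5.0% |

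With 10% missing at 6 months the gains are 1.2 points (R² = 0.05) and 2.4 points (R² = 0.10). The mean estimate was 0.400 to 0.401 against a true 0.4 throughout, so there is no bias under random dropout.

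**The case against.** The strongest reply is that the text already permits the adjustment. The covariate example is only illustrative, so sex and ethnicity could enter without amending anything. That is correct, and it makes this a missing commitment rather than an exclusion. It does not supply the commitment.

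The second reply is that the effect is small. Nothing in the documents says that sex or ethnicity predicts percent weight loss, the error is on the conservative side, and design power is kept. All of that stands, and it limits the point to minor.

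Two qualifications are also fair:
- The no-bias statement needs dropout unrelated to arm and strata. In a deliberately extreme simulation (35% against 5% dropout, crossed by arm and sex), omitting the strata shifted the 12-month estimate by about 0.02 SD at R² of 0.05 to 0.10, and adjusting removed the shift. This favours the adjustment.
- All the figures size the omission of the strata. They do not measure the effect of choosing covariates after seeing the data, and they do not show that an open list is harmless.

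The sensitivity analyses promised in section 6 sit in the missing-data paragraph and do not settle the covariate set.

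**Conclusion.** The concern holds, as a minor point. The primary model is not tied to the factors the trial randomises by, and the only stated route to adjustment would almost never select them. For an assumed R² of 0.05 to 0.10, the unadjusted standard error is 2.1% to 4.3% too large at a single time point. The power forgone is 1.4 to 2.8 points there, and about 1 to 2 points in the planned model. At R² = 0.02 it is 0.4 to 0.6 points, and at zero it is nil. The sample size of 256 is unaffected. These sizes rest on the assumed R² and on random dropout. The pre-specification gap rests on neither.

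**What to change.** In section 6, Aim 1, make three changes:

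1. State that the primary mixed model includes sex and ethnicity, as the stratification factors, as fixed covariates whatever the observed balance.
2. Name any other covariates in advance, or state that there are none.
3. Say that the bivariate baseline comparison is descriptive and is not a rule for choosing covariates.

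The cost is wording only. Both factors are already recorded for randomisation, the model gains two terms, and the sample size stays at 256. If the strata predict nothing the price is negligible: simulated power at R² = 0 is 86.0% with or without them.

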2.2 Primary and Secondary Aims

The primary aim (Aim 1) of the Aspire to Better Health study is to test the efficacy of a smartphone app plus health coaching intervention targeting weight loss vs. an attention control condition utilizing a device which tracks sleep.

The secondary aim (Aim 2) is to examine mediating variables of the intervention delivery on percent weight loss at 6 and 12 months. The mediators include adherence to self-monitoring, levels of discrimination, and dietary and physical activity (PA) self-efficacy. Finally, the third aim (Aim 3) will explore potential moderators of percent weight loss at 6 and 12 months, including depressive symptoms, ideal body image, and motivation for behavior change.

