Aim 2: We denote X = Independent variable, Y = Outcome measures, and M = Potential mediator. Mediation will be tested through first showing that X (e.g. intervention) is associated with both M (e.g., dietary self-efficacy) and Y (e.g., % weight change) using mixed-effects regression models as described above. Then, we will sequentially model the effect of X on Y, without and with adjusting for potential mediators. At last, we will use mediation path analysis to simultaneously regress (a) Y on M and X, and (b) M on X.. Estimates for the mediation effect will be derived using delta method or bootstrapping method if lack of normality is evident.²⁸ Adequacy fit of the path model is indicated by a non-significant χ^2 statistic, Comparative Fit Index (CFI) and Tucker-Levis Index (TLI) ≥ 0.9 , and a root mean square error approximation (RMSEA) ≤ 0.08 .

Aim 3: Similarly, we specify X = independent variable (e.g., intervention), Y = outcome variables (e.g., % weight change), and W = potential moderator (e.g., depressive symptoms). We will then test the significance of the moderating effect by including the interaction term of X and W in the mixed-effects regression models. A significant interaction between X and W suggest that the effect of X on Y changes at different levels of W.

Missing data: We will carefully examine the pattern of missing data and conduct appropriate multiple imputation if data are missing at random. If missing not at random is indicated, pattern mixture modeling will be used instead. Sensitivity analysis will be used to evaluate the robustness of study findings under different methods.

7. Data Management

REDCap data collection projects rely on a study-specific data dictionary defined in an iterative self-documenting process. REDCap supports electronic signatures by positively identifying the user through a unique username and password combination. The provisioning of accounts for system authentication is

integrated with the OSU Wexner Medical Center (OSUWMC) LDAP authentication service for studies containing protected health information (PHI) and is secured behind the OSUWMC firewall.

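### Aim 2 puts a significant intervention-outcome association ahead of the mediation test; that step is unnecessary, lowers power, and when it fails blocks all four mediators together

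*Combined protocol and SAP*

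**What the plan says.** Section 2.2 makes mediation of percent weight loss at 6 and 12 months the secondary aim and names four mediators: "The mediators include adherence to self-monitoring, levels of discrimination, and dietary and physical activity (PA) self-efficacy".

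Section 6, Aim 2 sets out three steps.

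1. The opening condition: "Mediation will be tested through first showing that X (e.g. intervention) is associated with both M (e.g., dietary self-efficacy) and Y". This uses the mixed models of Aim 1.
2. X on Y is then modelled without and with the mediators.
3. Last comes the path model: "we will use mediation path analysis to simultaneously regress (a) Y on M and X, and (b) M on X". The indirect effect is estimated by the delta method, or by bootstrap if the data are clearly non-normal.

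The text gives no significance level for step 1 and does not say what happens if it fails. Section 2.6 gives power only for the between-group comparison. No power is stated for Aim 2.

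**The concern.** This is a causal-steps sequence. The indirect effect is a × b, where a is the effect of X on the mediator and b is the effect of the mediator on Y given X. It can be real and detectable when the total effect is not significant, because the total effect also carries the direct path, which may be weak or opposed. Requiring a significant total effect adds a second hurdle that is not part of the hypothesis under test.

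The X-Y test is also common to every mediator. If it fails, and step 1 is applied as written, none of the four is tested. That is most likely when the total effect is smaller than planned, which is when information on mechanism would help explain the result.

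**Working it through.** **Inputs from the documents (Section 2.6).** "A sample size of 256 participants (n=128 per each trial arm) will have sufficient power (80%) to detect an" average difference of d = 0.4, with "two-sided significance level of 0.05 assuming 1) first-order autoregressive covariance structure", "the within-structure correlation of 0.8, and 3) 20% attrition rate at 12-month follow-up", and 1:1 allocation. Completers per arm: 128 × 0.8 = 102.4, taken as 102.

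**Inputs assumed.** The documents give no path sizes. I use a = 0.4 or 0.5 SD and b = 0.3, with within-arm SD of 1 for mediator and outcome. The direct effect is set to d − a × b, so the total effect equals d.

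**Plan's own figure.** n per arm = 2 × (1.96 + 0.842)² / 0.4² = 98.1, so 99 completers. 99 / 0.8 = 123.75, so 124 per arm and 248 in total. The t-test version gives 100 completers, 125 per arm and 250 in total. The stated 256 is therefore adequate. With 102 completers per arm, power is 81.5%.

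**Chance that the X-Y step passes.** Power = Φ(d × √(n/2) − 1.96), with √(102/2) = 7.141. The second column uses the mean of the 6- and 12-month values at correlation 0.8, with variance (1 + 0.8)/2 = 0.9, so d is divided by √0.9.

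| True total d | One time point | Mean of 6 and 12 months |
|---|---|---|
| 0.4 | Φ(0.897) = 81.5% | 85% |
| 0.3 | Φ(0.182) = 57% | 62% |
| 0.2 | Φ(−0.532) = 30% | 33% |

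These figures depend only on d and n, not on the assumed paths. Even if the planned effect is exactly true, the step fails in nearly one trial in five at a single time point (100 − 81.5 = 18.5%).

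**Power for the indirect effect.** Simulation of 20,000 trials per row, 102 per arm, one mediator and one outcome at one time point, b = 0.3. The joint test requires both a and b to be significant and stands in for a bootstrap interval. The step 1 condition is X-M and X-Y both at two-sided p < 0.05.

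| Total d | a | Joint test, no condition | Joint test, with condition | Delta method, no condition | Delta method, with condition |
|---|---|---|---|---|---|
| 0.4 | 0.4 | 80.8% | 68.1% | 71.7% | 60.9% |
| 0.4 | 0.5 | 93.8% | 76.9% | 88.9% | 73.5% |
| 0.3 | 0.4 | 80.4% | 48.8% | 71.5% | 44.3% |
| 0.3 | 0.5 | 94.0% | 54.7% | 89.1% | 52.4% |
| 0.2 | 0.4 | 80.6% | 26.8% | 71.8% | 24.6% |
| 0.2 | 0.5 | 93.5% | 29.0% | 88.8% | 28.1% |

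At d = 0.25 with a = 0.4, the joint test gives about 81% without the condition and 38% with it. Independent repeats agree to within one or two points; one gave 80% and 67% for the first row.

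**Which part of step 1 costs power.** The joint test already contains a significant a path, so the X-M condition removes nothing from it. For an interval on a × b in the first scenario, it lowers power only from 81.3% to 80.2%. The loss comes from the X-Y condition.

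**Is the X-Y step needed for error control?** With a = 0.5, b = 0 and direct effect 0.4, the joint test without the condition rejects in 4.8% of trials and the delta method in 2.0%. With a = 0 and b = 0.39, the figures are 5.0% and 3.8%. The indirect-effect test holds its level without help.

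**The case against.** The strongest reply is that the stopping rule is inferred. The second and third steps are stated without any condition, no threshold is attached to the first, and nothing says the path model is dropped if it fails. The path model with a delta-method or bootstrap estimate, which is the right analysis, is already planned. This stands: the text is ambiguous rather than explicit. It does not remove the point. Either step 1 is a precondition, with the losses shown, or its consequence is undefined and could be settled after the total effect is known. The same edit resolves both.

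A reader might infer more than the documents support:

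- **That Aim 2 cannot study mechanism if the effect is smaller than planned.** The X-Y step still passes 57% of the time at d = 0.3 and 30% at d = 0.2, and the path model remains in the plan.
- **That both parts of step 1 lose power.** The X-M part costs almost nothing.
- **That a true mediator is usually missed.** At the planned d = 0.4 the loss in the table is 11 to 17 points. The severe losses need a total effect well below plan.

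The point about repeated measures also stands in part: using both visits makes the X-Y step pass somewhat more often, with the same pattern.

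Two further objections change the remedy. First, adherence to self-monitoring (Table 4) is tracked by the health coach through Ascend, and controls receive Lose It! only at the 12-month visit (Section 3.8). It has no real control-arm values, so neither the simulation nor an ordinary a × b applies to it. Second, the X-Y condition gives incidental protection against multiple testing. For three mediators with b = 0, tested independently at 5%, the chance of at least one false positive is 1 − 0.95³ = 14%. With two time points, treated as independent, it is 1 − 0.95⁶ = 26%.

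**Conclusion.** The point holds in a limited form. On a plain reading, Section 6 makes a shown X-Y association a precondition for testing mediation. That step is unnecessary for a valid test of the indirect effect and applies to all four mediators at once.

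The cost is moderate at the planned effect (about 81% to 68% by the joint test and 72% to 61% by the delta method, with a = 0.4 and b = 0.3) and large if the true effect is about half of plan. The power figures rest on assumed path sizes, normal data, one time point and 102 completers per arm. The pass rates for the X-Y step do not depend on the path sizes. Only the secondary aim is affected; Aim 1 is not.

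**What to change.** In Section 6, Aim 2:

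- Remove the X-Y association as a prerequisite. State that the test of mediation is the indirect effect a × b with its confidence interval from the planned path model, reported whatever the significance of the total effect.
- Report a, b, the direct effect and the total effect alongside it.
- Apply this to the mediators measured in both arms: dietary self-efficacy, physical activity self-efficacy and discrimination.
- Specify a separate analysis for adherence to self-monitoring, because controls do not receive Lose It! before the 12-month visit.
- Acknowledge or adjust for multiplicity across mediators and the two time points.

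The change is to SAP wording, with no new data or visits. The cost is that more indirect effects are reported, so the multiplicity statement has to accompany the change.
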